## **4. SUBJECT DISPOSITION**

### **4.1. Subject Enrollment and Disposition**

A summary of subject disposition will be provided by treatment group and overall. This summary will present the number of subjects screened, the number of subjects randomized, and the number of subjects in each of the categories listed below, for overall and each study phase (double-blind and open-label):

- Safety Analysis Set
- Completed study drug
- Did not complete study drug with reasons for premature discontinuation of study drug
- Completed study
- Did not complete study with reasons for premature discontinuation

For the status of study drug and study completion, and reasons for premature discontinuation, the number and percentage of subjects in each category will be provided. The denominator for the percentage calculation will be the total number of subjects in the All Randomized Analysis Set corresponding to that column.

### **4.2. Extent of Study Drug Exposure and Adherence**

Extent of exposure to study drug will be examined by assessing the total duration of exposure to study drug.

#### **4.2.1. Duration of Exposure to Study Drug**

Total duration of exposure to study drug will be defined as last dosing date minus first dosing date plus 7, regardless of any temporary interruptions in study drug administration, and will be expressed in days. If the last study drug dosing date is missing, the latest study drug end date, clinical visit date, laboratory sample collection date, or vital signs assessment date that occurred during the on-treatment period will be used.

The total duration of exposure to study drug will be summarized using descriptive statistics and using the number (ie, cumulative counts) and percentage of subjects exposed through the following time periods: baseline (Day 1), Week 1 (Day 8), Week 4 (Day 29), Week 8 (Day 57), Week 12 (Day 85), Week 16 (Day 113), Week 20 (Day 141), and Week 24 (Day 169). Summaries will be provided by treatment group for the Safety Analysis Set. No formal statistical testing is planned.

#### **4.2.2. Adherence to Study Drug**

A summary of adherence to study drug will not be provided.

A by-subject listing of study drug administration will be provided by subject ID number (in ascending order) and visit (in chronological order).

#### **4.3. Deviations**

A by-subject listing will be provided for those subjects who did not meet at least 1 eligibility (inclusion or exclusion) criterion. The listing will present the eligibility criterion (or criteria if more than 1 deviation) that subjects did not meet and related comments, if collected.

## **5. BASELINE CHARACTERISTICS**

### **5.1. Demographics**

Subject demographic variables (ie, age, sex, race, and ethnicity) will be summarized by treatment group and overall using descriptive statistics for age, and using number and percentage of subjects for sex, race, and ethnicity. The summary of demographic data will be provided for the All Randomized Analysis Set.

A by-subject listing of demographics, including the informed consent date, will be provided by subject ID number in ascending order.

### **5.2. Other Baseline Characteristics**

Other baseline characteristics include body weight (in kg), height (in cm), body mass index (BMI; in  $\text{kg}/\text{m}^2$ ), genotype, and pre-bronchodilator and post-bronchodilator spirometry measurements. These baseline characteristics will be summarized by treatment group and overall using descriptive statistics for continuous variables and using number and percentage of subjects for categorical variables. The summary of baseline characteristics will be provided for the All Randomized Analysis Set. No formal statistical testing is planned.

A by-subject listing of other baseline characteristics will be provided by subject ID number in ascending order.

### **5.3. Medical History**

The summaries of medical history will not be provided.

## **6. EFFICACY ANALYSES**

### **6.1. Primary Efficacy Endpoint**

The primary endpoint is the absolute change in pre-bronchodilator FEV1 percent predicted from Baseline to Week 8.

The NHANES III {Hankinson 1999} method will be used to calculate the FEV1 percent predicted value.

#### **6.1.1. Statistical Hypothesis for the Primary Efficacy Endpoint**

No statistical hypotheses will be tested.

#### **6.1.2. Analysis of the Primary Efficacy Endpoint**

The descriptive statistics (n, mean, standard deviation [SD], median, Q1, Q3, minimum, and maximum) for the absolute values and absolute change in pre-bronchodilator FEV1 percent predicted will be presented for each post-baseline time point including open-label period.

### **6.2. Secondary Efficacy Endpoints**

#### **6.2.1. Definitions of Key Secondary Efficacy Endpoints**

The secondary efficacy endpoints include:

- The absolute change in post-bronchodilator FEV1 percent predicted from Baseline to Week 8
- The relative change in pre-bronchodilator FEV1 percent predicted from Baseline to Week 8
- The relative change in post-bronchodilator FEV1 percent predicted from Baseline to Week 8.

The relative change of FEV1 % predicted from baseline to Week 8 is calculated as the [absolute change from baseline to Week 8 / baseline FEV1 % predicted value] x 100.

#### **6.2.2. Analysis Methods for Secondary Efficacy Endpoints**

Descriptive statistics (n, mean, standard deviation [SD], median, Q1, Q3, minimum, and maximum) for absolute change and relative change in post-bronchodilator FEV1 percent predicted from baseline, as well as relative change in pre-bronchodilator FEV1 percent predicted from baseline, will be provided for each post-baseline time point including open-label period.

### **6.3. Other Efficacy Endpoints**

Other efficacy endpoints will not be analyzed.

## **7. SAFETY ANALYSES**

### **7.1. Adverse Events and Deaths**

#### **7.1.1. Adverse Event Dictionary**

Clinical and laboratory adverse events (AEs) will be coded using the current version of MedDRA. System organ class (SOC), high-level group term (HLGT), high-level term (HLT), preferred term (PT), and lower-level term (LLT) will be provided in the AE dataset.

#### **7.1.2. Adverse Event Severity**

Adverse events are graded by the investigator as Grade 1, 2, 3, or 4 according to toxicity criteria specified in the protocol. The severity grade of events for which the investigator did not record severity will be categorized as “missing” for tabular summaries and data listings. The missing category will be listed last in summary presentation.

#### **7.1.3. Relationship of Adverse Events to Study Drug**

Related AEs are those for which the investigator selected “Related” on the AE CRF to the question of “Related to Study Treatment.” Relatedness will always default to the investigator’s choice, not that of the medical monitor. Events for which the investigator did not record relationship to study drug will be considered related to study drug for summary purposes. However, by-subject data listings will show the relationship as missing.

#### **7.1.4. Serious Adverse Events**

Serious adverse events (SAEs) will be identified and captured as SAEs if AEs met the definitions of SAE specified in the study protocol. Serious adverse events captured and stored in the clinical database will be reconciled with the SAE database from the Gilead Drug Safety and Public Health Department before data finalization.

#### **7.1.5. Treatment-Emergent Adverse Events**

##### **7.1.5.1. Definition of Treatment-Emergent Adverse Events**

Treatment-emergent adverse events (TEAEs) are defined as 1 or both of the following:

- Any AEs with an onset date on or after the study drug start date and no later than 30 days after permanent discontinuation of study drug
- Any AEs leading to premature discontinuation of study drug.

#### 7.1.5.2. Incomplete Dates

If the onset date of the AE is incomplete and the AE stop date is not prior to the first dosing date of study drug, then the month and year (or year alone if month is not recorded) of onset determine whether an AE is treatment emergent. The event is considered treatment emergent if both of the following 2 criteria are met:

- The AE onset date is the same as or after the month and year (or year) of the first dosing date of study drug, and
- The AE onset date is the same as or before the month and year (or year) of the date corresponding to 30 days after the date of the last dose of study drug

An AE with completely missing onset and stop dates, or with the onset date missing and a stop date later than the first dosing date of study drug, will be considered to be treatment emergent. In addition, an AE with the onset date missing and incomplete stop date with the same or later month and year (or year alone if month is not recorded) as the first dosing date of study drug will be considered treatment emergent.

#### 7.1.6. Summaries of Adverse Events and Deaths

Treatment-emergent (TE) AEs will be summarized based on the Safety Analysis Set.

The AEs will be reported by the treatment period. If subject does not continue into the open-label period then all TEAEs will be reported in the double-blind period summaries. For subjects who continue into the open-label phase, all TEAEs during the double-blind treatment phase are the AEs started prior to the first dose of open-label treatment. The AEs with the onset date on or after the first dose of the open-label treatment and no later than 30 days after permanent discontinuation of study drug will be reported in the open-label summaries.

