#### **3.1. Analysis Sets**

Analysis sets define the subjects to be included in an analysis. Analysis sets and their definitions are provided in this section. The analysis set will be identified and included as a subtitle of each table, figure, and listing.

For each analysis set, the number and percentage of subjects eligible for inclusion will be summarized by treatment group.

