##### **3.1.3. Safety Analysis Set**

The Safety Analysis Set includes all subjects who took at least 1 dose of study drug. This is the primary analysis set for safety analyses.

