##### 7.1.6.1. Summaries of AE incidence in Combined Severity Grade Subsets

For TEAEs described below, summaries will be provided by SOC, PT, treatment group, and study phase:

- All TE treatment-related AEs
- All TE SAEs
- All TEAEs leading to premature discontinuation of study drug
- TEAEs of Interest:
  - injection site reactions (based on Gilead medical search terms provided by DSPH)

A brief, high-level summary of AEs described above will also be provided by treatment group and study phase.

In addition to the above summary tables, all TEAEs will be summarized by PT only, in descending order of total frequency. Summaries of all TEAEs by SOC, PT and maximum severity will also be provided.

Multiple events will be counted only once per subject in each summary. Adverse events will be summarized and listed first in alphabetic order of SOC and PT in descending order of total frequency within each SOC. For summaries by severity grade, the most severe grade will be used for those AEs that occurred more than once in an individual subject during the study.

In addition, data listings will be provided for the following:

- All AEs, indicating whether the event is treatment emergent
- SAEs
- Deaths
- AEs leading to premature discontinuation of study drug

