#### 7.2.2.2. Summaries of Laboratory Abnormalities

The summaries (number and percentage of subjects) for treatment-emergent laboratory abnormalities will be provided by lab test, treatment group and study phase; subjects will be categorized according to the most severe postbaseline abnormality grade for a given lab test.

For all summaries of laboratory abnormalities, the denominator is the number of subjects with nonmissing postbaseline values within study period.

A by-subject listing of treatment-emergent laboratory abnormalities will be provided by subject ID number and visit in chronological order. This listing will include all test results that were collected throughout the study for the lab test of interest, with all applicable severity grades displayed.

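### Open-label disposition percentages, and by implication open-label adverse-event percentages, are based on sets that include subjects who never entered the optional extension

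*SAP*

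**What the plan says.** SAP 3.1 explains that "Analysis sets define the subjects to be included in an analysis" and defines three sets: All Randomized, Full and Safety. None requires an open-label dose. For the safety set, SAP 3.1.3 says: "The Safety Analysis Set includes all subjects who took at least 1 dose of study drug".

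Disposition (SAP 4.1) is to be shown "for overall and each study phase (double-blind and open-label"). For study drug and study completion, and for reasons for stopping, "The denominator for the percentage calculation will be the total number of subjects in the All Randomized Analysis Set" belonging to the column in question.

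For adverse events, SAP 7.1.6 states: "Treatment-emergent (TE) AEs will be summarized based on the Safety Analysis Set". Under SAP 7.1.6.1, "summaries will be provided by SOC, PT, treatment group, and study phase". The open-label tables take "The AEs with the onset date on or after the first dose of the open-label treatment", up to 30 days after permanent discontinuation. All treatment-emergent events of a subject who does not continue go to the double-blind tables.

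The extension is optional (Protocol 3.3.3; SAP 1.2), and the SAP provides for subjects who do not roll over (SAP 1.2, 3.8.1, 7.1.6). For laboratory abnormalities, SAP 7.2.2.2 uses a base tied to the period: "the denominator is the number of subjects with nonmissing postbaseline values within study period".

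**The concern.** In the double-blind phase the named sets fit, because every randomized and dosed subject starts there. In the open-label phase they do not. A subject who declined the extension, or left before it, cannot contribute an open-label event or an open-label completion, but remains in the All Randomized and Safety sets. The numerator is limited to entrants and the denominator is not.

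The report is purely descriptive, so the counts and percentages are the result. Placebo subjects who enter from Part 1 receive 600 mg for the first time in the extension. Their open-label events, including the injection-site reactions that SAP 7.1.6.1 singles out, are their first experience on active drug. Disposition has a further gap. The listed categories contain no row for entering the extension, and the SAP does not say whether a non-entrant counts under completion or non-completion of open-label drug, or under neither.

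**Working it through.** The documents state no open-label count or percentage, so there is no planned figure to reproduce. The check is a direct proportion.

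**Inputs**
- N, subjects randomized or dosed: 6 enrolled (SAP 1.2 and 1.3). I assume all 6 were randomized and dosed, so that both sets have N = 6.
- m, subjects with at least 1 open-label dose: not given. I assume a range of 2 to 6.
- k, entrants with the open-label event, or who complete the open-label phase.

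**Formulas**
- Percentage under the SAP read literally: k / N
- Percentage among those at risk: k / m
- Ratio of the first to the second: (k / N) / (k / m) = m / N

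The ratio does not depend on k. It is below 1 whenever m < N and equals 1 only when m = N. With k = 0, both percentages are zero.

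**Results for N = 6**

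| m (assumed) | m / N | One event, SAP base (1/6) | One event, entrants (1/m) | All entrants complete, SAP base (m/6) | All entrants complete, entrants (m/m) |
|---|---|---|---|---|---|
| 2 | 0.33 | 16.7% | 50.0% | 33.3% | 100% |
| 3 | 0.50 | 16.7% | 33.3% | 50.0% | 100% |
| 4 | 0.67 | 16.7% | 25.0% | 66.7% | 100% |
| 5 | 0.83 | 16.7% | 20.0% | 83.3% | 100% |
| 6 | 1.00 | 16.7% | 16.7% | 100% | 100% |

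The tables are by treatment group, so the same factor acts within an arm. The actual split is not given. If an arm had 3 subjects and 1 entered and had the event, the table would show 1/3 = 33.3% against 1/1 = 100%. At that size neither percentage is informative; the example shows only the mechanism.

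**How firm each denominator is**
- Disposition: explicit. SAP 4.1 names the set and applies it to a display that includes the open-label phase.
- Adverse events: implied. SAP 7.1.6 names the set but writes no denominator. It follows from SAP 3.1, where a set fixes who is in the analysis, and from SAP 3.1.3, where any dose qualifies.

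**The case against.** The strongest reply is that the AE denominator is never written down. Where the SAP wants to fix one it does so, as in 4.1 and 7.2.2.2. SAP 4.1 also lists the Safety Analysis Set among the categories shown for each phase. Repeating that row by phase makes most sense if the open-label row counts subjects dosed in that phase, which would point to a phase-specific AE base and come close to giving the number entering. The tie to each column in SAP 4.1 leaves similar room for disposition. This stands to the extent that the AE part is an inference, and a programmer might build the table correctly. It does not remove the point: the sets as defined are not restricted to entrants, and the columns described are treatment group and overall.

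A second reply is that the share of randomized subjects who complete the extension is a legitimate quantity. That is so if it is labelled as such. It is not a completion rate among those who entered.

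A reader might also infer that the AE and laboratory denominators contradict each other and must match. The documents do not support that. A laboratory abnormality needs a measured value and an adverse event does not, so the two bases can properly differ. SAP 7.2.2.2 shows only that a period-specific base was considered elsewhere. Nor can the concern be extended to exposure: SAP 4.2.1 plans total duration and cumulative counts, with no exposure table by phase.

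Finally, the practical harm is limited. By-subject listings of all adverse events (SAP 7.1.6.1) and of study drug administration (SAP 4.2.2) allow a recount.

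**Conclusion.** The point holds as a minor one. Read literally, open-label disposition percentages, and by implication open-label AE percentages, are multiplied by m / N. They are therefore understated if any subject did not enter the extension and at least one entrant completed or had an event. With N = 6 the factor runs from 0.33 to 0.83 for an assumed 2 to 5 entrants, and it is 1.00 if all 6 entered. The true size is unknown because the number entering is not given.

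It would be tempting to conclude that open-label safety on 600 mg is materially misreported. The documents do not support that: the effect may be zero, there are 6 subjects, SAP 1.3 and 6.1.1 rule out inferential analysis, and the listings allow every figure to be recounted. No inference or decision changes.

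**What to change.** - Add to SAP 3.1 an open-label safety set: subjects who took at least 1 open-label dose.
- In SAP 7.1.6, name it as the denominator for open-label AE percentages. Keep the Safety Analysis Set for the double-blind tables.
- In SAP 4.1, use it as the denominator for open-label completion and discontinuation percentages. Keep All Randomized for the overall and double-blind displays.
- Add a disposition row for the number entering the extension, as a percentage of All Randomized, so that non-entry is visible and is not mistaken for premature discontinuation.

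The exposure summary and the laboratory denominator need no change on this account.

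The cost is one definition, one denominator rule for the open-label tables and one extra row, with no new data. If the SAP is already final, SAP 1 provides for documenting the change in the clinical study report.

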##### 7.1.6.1. Summaries of AE incidence in Combined Severity Grade Subsets

For TEAEs described below, summaries will be provided by SOC, PT, treatment group, and study phase:

- All TE treatment-related AEs
- All TE SAEs
- All TEAEs leading to premature discontinuation of study drug
- TEAEs of Interest:
  - injection site reactions (based on Gilead medical search terms provided by DSPH)

A brief, high-level summary of AEs described above will also be provided by treatment group and study phase.

In addition to the above summary tables, all TEAEs will be summarized by PT only, in descending order of total frequency. Summaries of all TEAEs by SOC, PT and maximum severity will also be provided.

Multiple events will be counted only once per subject in each summary. Adverse events will be summarized and listed first in alphabetic order of SOC and PT in descending order of total frequency within each SOC. For summaries by severity grade, the most severe grade will be used for those AEs that occurred more than once in an individual subject during the study.

In addition, data listings will be provided for the following:

- All AEs, indicating whether the event is treatment emergent
- SAEs
- Deaths
- AEs leading to premature discontinuation of study drug

## **7.2. Laboratory Evaluations**

A by-subject listing for laboratory test results will be provided by subject ID number and visit in chronological order for hematology and serum chemistry separately. Values falling outside of the relevant reference range and/or having a severity grade of 1 or higher on the Gilead Grading Scale for Severity of Adverse Events and Laboratory Abnormalities [CTCAE severity grade] will be flagged in the data listings, as appropriate

No formal statistical testing is planned.

### **7.2.1. Summaries of Numeric Laboratory Results**

In the case of multiple values in an analysis window, data will be selected for analysis as described in Section 3.8.3.

Descriptive statistics for laboratory tests will not be presented.

### **7.2.2. Graded Laboratory Values**

The Common Toxicity Criteria for Adverse Events (CTCAE) Version 4.03 will be used for assigning toxicity grades to laboratory results for analysis. Grade 0 includes all values that do not meet the criteria for an abnormality of at least Grade 1. For laboratory tests with criteria for both increased and decreased levels, analyses for each direction (ie, increased, decreased) will be presented separately.

#### 7.2.2.1. Treatment-Emergent Laboratory Abnormalities

Treatment-emergent laboratory abnormalities are defined as values within the reference range at baseline, but which become lower or higher than the reference range or values had a directional change in abnormality from baseline (eg, the value low at baseline became high at postbaseline visit) at any postbaseline time point, up to and including the date of last dose of study drug plus 30 days. If the relevant baseline laboratory value is missing, any postbaseline laboratory value that is lower or higher than the reference range will be considered treatment emergent.

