8.6.3. Laboratory Evaluations

Selected laboratory data (using conventional units) will be summarized using only observed data. Data and change from Baseline at all scheduled time points will be summarized.

Graded laboratory abnormalities will be defined using the grading scheme in Section 7.5.

Incidence of treatment-emergent laboratory abnormalities, defined as values that increase at least one toxicity grade from Baseline at any time post Baseline will be summarized. If Baseline data are missing, then any graded abnormality (ie, at least a Grade 1) will be considered treatment emergent.

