#### 7.7. Changes From Protocol-Specified Safety Analyses

The limited efficacy and safety summaries are provided due to low number of subjects enrolled prior to the study termination.

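### The SAP replaces the protocol's grade-increase definition of a treatment-emergent laboratory abnormality with a reference-range rule, does not declare the change, and so leaves out worsening from an abnormal baseline

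*SAP*

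**What the plan says.** Protocol 8.6.3 defines treatment-emergent laboratory abnormalities as "values that increase at least one toxicity grade from Baseline at any time post Baseline". For a missing baseline it adds: "If Baseline data are missing, then any graded abnormality (ie, at least a Grade 1) will be considered treatment emergent".

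SAP 7.2.2.1 gives a different definition: "values within the reference range at baseline, but which become lower or higher than the reference range or values had a directional change in abnormality", and its example of a directional change is a low value that later becomes high. If baseline is missing, any out-of-range postbaseline value counts, graded or not. The SAP also sets a time limit, "up to and including the date of last dose of study drug plus 30 days", where the protocol sets none after Baseline.

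SAP 7.2.2 assigns CTCAE version 4.03 grades to the results and states that "Grade 0 includes all values that do not meet the criteria for an abnormality of at least Grade 1". SAP 7.2.2.2 then builds a table and a by-subject listing on the 7.2.2.1 definition. In the table, "subjects will be categorized according to the most severe postbaseline abnormality grade for a given lab test", and "the denominator is the number of subjects with nonmissing postbaseline values within study period".

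The whole of SAP 7.7, headed as changes from the protocol's safety analyses, is one sentence: "The limited efficacy and safety summaries are provided due to low number of subjects enrolled prior to the study termination".

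**The concern.** The two documents define the same event differently, and the SAP does not say so. Its sentence in 7.7 explains why there are fewer outputs. It does not explain a different event definition inside an output that was kept.

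The change has consequences in both directions. A subject with an abnormal baseline who worsens on the same side is not counted. A subject who moves from in range to slightly out of range, with no CTCAE grade, is counted in a table organised by grade, where the only place for the result is Grade 0.

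Abnormal baselines are foreseeable. Protocol 4.3 excludes AST, ALT, GGT or alkaline phosphatase only above 3 x ULN at Screening, and bilirubin only above 2 x ULN. Subjects who enter with raised liver tests stay in the denominator but cannot enter the numerator for a further rise. SAP 7.2.1 drops descriptive statistics for laboratory tests, so no other summary would show that rise.

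**Working it through.** The documents give no figure to reproduce, so the check sets the two rules side by side and enumerates what each counts.

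| Element | Protocol 8.6.3 | SAP 7.2.2.1 |
|---|---|---|
| Basis | CTCAE grade | Reference range |
| In range to out of range, ungraded | Not counted | Counted |
| In range to Grade 1 or higher | Counted | Counted |
| Abnormal, then worse on the same side | Counted if the grade rises | Not counted |
| Low/high switch | Counted if the new value is graded | Counted |
| Missing baseline | Grade 1 or higher | Any out-of-range value |
| Time limit | None after Baseline | Last dose plus 30 days |

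**By grade alone, one direction.** Take Grades 0 to 4, with Grade 0 in range and Grade 1 or higher out of range.

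- Protocol (any rise of at least one grade): 4 + 3 + 2 + 1 = 10 shifts.
- SAP (in range to out of range): 4 shifts, from 0 to 1, 2, 3 or 4.
- Missed by the SAP: 10 − 4 = 6, namely 1→2, 1→3, 1→4, 2→3, 2→4 and 3→4. Five of these end at Grade 3 or 4 (all except 1→2).

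**With Grade 0 split.** Under SAP 7.2.2 a value can be out of range and still Grade 0. The states become: in range, out of range ungraded, and Grades 1, 2, 3 and 4.

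- Protocol: 4 (from in range) + 4 (from out of range ungraded) + 3 + 2 + 1 = 14 patterns.
- SAP: in range to any of 5 out-of-range states = 5 patterns.
- Shared: 4 (in range to Grades 1 to 4).
- Protocol only: 14 − 4 = 10, made up of 4 from out of range ungraded and 6 from Grades 1 to 3.
- SAP only: 5 − 4 = 1 (in range to out of range ungraded).

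**With an opposite-side baseline added.** For tests graded in both directions, a baseline abnormal on the other side is Grade 0 for the direction analysed.

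- Protocol: 14 + 4 = 18 patterns.
- SAP: 5 + 5 = 10 patterns.
- Shared: 4 + 4 = 8.
- Protocol only: 18 − 8 = 10, unchanged.
- SAP only: 10 − 8 = 2.

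**Illustration.** Suppose ALT is 2.5 x ULN at baseline, a level allowed at Screening, and later reaches 9 or 21 x ULN. The baseline was not in range and the direction has not switched, so under the SAP neither rise is treatment-emergent.

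**Scale.** Six subjects were enrolled. If all six have postbaseline values, one omitted subject is 1/6 = 17% overall. The documents do not give the split by arm. If it were 3:3, one omitted subject would be 1/3 = 33% of an arm.

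**The case against.** The strongest case against is that little turns on this. The study stopped after 6 subjects, and the SAP supports a synoptic report with no inference. SAP 7.2 lists every hematology and chemistry result by subject and flags values that are out of range or graded, and liver tests are presented within chemistry. A rise from Grade 1 to Grade 3 would therefore be printed and flagged, only not labelled treatment-emergent. Under Protocol 7.5, abnormalities that need intervention or change study drug are also recorded as adverse events, and SAP 7.1.6.1 lists all adverse events. If the same subject and test qualify by another route, the treatment-emergent listing prints all results for that test. All of this stands, and it limits the effect.

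It is also fair that the pattern counts give every cell equal weight, depend on how grades relate to the reference range, and change when opposite-side baselines are added. They show which cases the rule cannot see, not how often those cases occur. The 10 missed patterns do not change when opposite-side baselines are added.

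The liver limits apply at Screening, while the analysis baseline is the last value on or before first dose. They show that an abnormal baseline is possible, not that one occurred.

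The 30-day window is secondary. It is a reasonable limit that needs only to be declared.

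None of this restores the omitted cases to the table. The SAP's own low-to-high example also rules out reading a directional change as same-side worsening.

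**Conclusion.** The concern holds. SAP 7.2.2.1 departs from Protocol 8.6.3, SAP 7.7 does not declare it, and following the SAP as written would leave same-direction worsening from an abnormal baseline out of the treatment-emergent count. In one direction the rule misses 6 of 10 upward grade shifts, or 10 of 14 patterns when ungraded out-of-range values are treated as a separate state. Both counts assume that a graded value lies outside the reference range.

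Graded same-direction worsening is undercounted. The net direction for the whole table is not established, because ungraded out-of-range values push its counts up. The documents do not say whether any of the 6 subjects had an abnormal baseline or worsened. The point should be fixed because the table would be wrong by the protocol's own definition and the correction is cheap, but its practical effect on this report is limited.

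**What to change.** In SAP 7.2.2.1, define treatment-emergent as an increase of at least one CTCAE grade from baseline, assessed separately for each direction, at any postbaseline time point up to and including last dose plus 30 days. If baseline is missing, count any value of Grade 1 or higher. Keep the table by worst grade, and leave ungraded out-of-range values to the flagged listing in SAP 7.2. State in SAP 7.7 that the 30-day limit differs from the protocol, which sets none.

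Two lighter options go only part of the way. Adding a grade-increase limb to the existing rule would recover the omitted cases, but ungraded values would stay in a table organised by grade. Declaring the present definition in 7.7 would make the change visible but would not count the omitted cases.

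The cost is wording in two SAP sections and a standard derivation. The grades are already assigned under SAP 7.2.2, and no new data are needed.
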